3.3. Computing Environment

All descriptive statistical analyses will be performed using SAS statistical software Version 9.3 (or later), unless otherwise noted. Medical history and AEs will be coded using the Medical Dictionary for Regulatory Activities (MedDRA) Version 18.0 (or later). Concomitant medications will be coded using the World Health Organization (WHO) Drug Dictionary Version March 2015 (or later).

3.4. Baseline Definitions

For the mNIS+7/NIS+7 individual components, total scores and related endpoints, the Screening/Baseline and Baseline visits were performed on separate days. Baseline will be calculated as the average of 2 replicate measures each assessed at the Screening/Baseline and Baseline visits. For grip strength and 10m walk test, if replicate measures are obtained at the Screening/Baseline and Baseline visits, baseline will also be calculated as the average of the 2 replicates.

For PD parameters (TTR, RBP, Vitamin A), baseline will be defined as the average of all records, including those from any unscheduled visits, prior to the date and time of first dose.

For all other parameters, unless noted otherwise, baseline will be defined as the last non-missing measurement on or prior to the first dose of study treatment.

3.5. Randomization Stratification Factors

Stratification factors for randomization include Neuropathy Impairment Score (NIS; < 50 vs. ≥ 50), early onset V30M (< 50 years of age at onset) vs. all other mutations (including late onset V30M), and previous tetramer stabilizer use (tafamidis or diflunisal) vs. no previous tetramer stabilizer use.

Stratification factors are recorded in both the IVR and the clinical database. In statistical analyses that use randomization stratification factors as covariates, the stratum assignment will reflect the values as recorded in the clinical database. In the presence of stratification errors, the stratification used in analysis may not match that in the IVR.

3.6. Multiple Comparisons/Multiplicity

Type I error control for secondary endpoints will be achieved by a hierarchical ordering procedure. Endpoints will be tested in the following pre-specified hierarchy:

1. Norfolk QOL-DN questionnaire [Total Score]
2. NIS-W score
3. R-ODS
4. 10-meter walk test speed
5. mBMI
6. COMPASS-31 total score

Only if a comparison is significant at a 2-sided 0.05 significance level, the next endpoint in the hierarchy may be formally tested; if a given comparison is not significant at a 2-sided 0.05 significance level, the subsequent tests will be performed and the results summarized, but statistical significance will not be inferred.

3.7. Initiation of Alternative Treatment for FAP

Rapid progression patients have the option to discontinue study drug, receive alternative FAP treatment, and return for their 18-month efficacy assessment. Non-rapid progressors may also initiate alternative FAP treatment during study, although this would be a major protocol violation. Alternative FAP treatment may confound the efficacy outcome. For the primary analysis of mNIS+7, Norfolk QOL-DN and NIS-W, the assessments collected after alternative FAP treatment (liver transplant or use of tafamidis or diflunisal for more than 14 days) will be

treated as missing. The data post alternative FAP treatment will be included in efficacy listings with a footnote and will also be used in sensitivity analyses as specified.

For all other efficacy endpoints, data collected post alternative FAP treatment will be included in analyses.

A separate listing will be provided for patients who initiate alternative treatment for FAP while on study.

3.8. Missing Data with Efficacy Endpoints

All efficacy data collected during study, regardless of whether before or after treatment discontinuation, will be included for analyses, with the exception of mNIS+7, Norfolk QOL, and NIS-W assessments collected post alternative FAP treatment (discussed in Section 3.7).

3.8.1. Missing Subcomponents within Primary and Secondary Efficacy Endpoints

For each patient, missing subcomponents within the primary mNIS+7 endpoint and secondary efficacy endpoints will be imputed whenever possible according to the algorithm specified in Appendix 7.2.1 through Appendix 7.2.5. When this “partial imputation” is successful (i.e., complete mNIS+7 values are produced), these values will be used in all statistical analyses. When partial imputation is unsuccessful, the efficacy endpoint will be treated as completely missing.

3.8.2. Summary of Missing Data

For each of the primary and secondary efficacy endpoints, the number and percentage of missing data (completely missing) at each visit (baseline, 9-month, and 18-month) will be summarized by study arm.

Time to treatment discontinuation will be estimated descriptively using Kaplan-Meier method by treatment arm. Patients completing study treatment will be censored at the last dose of study drug.

Spaghetti plots will be presented to display the trajectories over time for individual patient’s change from baseline in mNIS+7 and Norfolk QOL-DN for patients who have missing 18-month assessments.

3.8.3. Handling of Missing Data

For the primary and secondary efficacy endpoints, the primary analysis will be based on the mixed-effects model repeated measures (MMRM) method, which makes use of fully and partially observed data sequences from individual patients by estimating the covariance between data from different time points. The MMRM will be implemented using an unstructured approach to modeling both the treatment-by-time means and the (co)variances, leading to what is essentially a multivariate normal model wherein treatment arm means at the primary time point are adjusted to reflect both the actually observed data and the projected outcomes from the patients with missing data [11]. In this primary analysis, missing data will not be imputed and are assumed to be missing-at-random (MAR).

For the primary endpoint mNIS+7 and the first secondary endpoint Norfolk QOL, sensitivity analyses will be conducted to assess the impact of missing data as discussed in Section 4.3.

3.9. Visit Windows

It is expected that all visits should occur according to the protocol schedule. All data will be tabulated and analyzed per the evaluation visit as recorded on the electronic case report form (eCRF) even if the assessment is outside of the visit window.

For efficacy assessments, if the scheduled 9-month or 18-month visits are not performed, the unscheduled and/or discontinuation visits will be grouped with the 9-month or 18-month assessments if they are performed within 3 months of the scheduled assessment. The derived visits will be used for all analyses.

Unless otherwise specified above, data collected at unscheduled visits will be included in by-patient data listings and figures, but no assignment to a study visit will be made for the purpose of by-visit summary tabulations. However, unscheduled visits may be used in the calculation of baseline values (as discussed in Section 3.4) and for inclusion in any categorical shift summaries (e.g., shift from baseline to “worst” post-baseline value).

3.10. Interim Analyses

No interim analysis was conducted for this study.

3.11. Final Analyses

After the last patient completes the 18-month efficacy assessment or the 18-month efficacy visit window per protocol has elapsed, the sponsor will prepare for the final analysis. The study will then be unblinded and the final analysis will be conducted. If there is additional safety data collected after the final analysis, the data will be presented in listings only.

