6.2.2 Routine Study Visits

The procedures described below are to be performed for all routine study visits (from Day 21 through Day 546), with the exception of the 9-month and 18-month efficacy assessments (occurring on Days 253-272 and Days 553-560, respectively). All visits have a window of "±3 days" except for the Day 273 visit which has a window of "+3 days" to allow adequate time for the assessment of the patient's 9-month mNIS+7 and FAP stage testing, which will determine if the patient met the criteria for Rapid Disease Progression.

Patients will undergo the following procedures before study drug dosing:

- At all dosing visits, administer premedications at least 60 minutes prior to the start of administration of study drug (see [Section 5.3.1](#));
- At all dosing visits, measure weight;
- At all dosing visits, measure vital signs;

- On Days 252 and 546, perform a physical examination;
- On Days 126 and 399, perform a 12-lead ECG;
- On Days 21, 126, 252, 273, 399, and 546, collect blood sample for serum TTR protein, RBP, and vitamin A. Additionally, aliquots of serum samples will be taken for long-term frozen storage, to permit testing of additional proteins related to FAP;
- On Days 84, 189, 357, 462, and 546, collect blood samples for serum chemistry tests;
- On Day 546, collect blood sample for INR;
- On Days 21, 126, 252, 399, and 546, collect a blood sample for anti-drug antibody assessment;
- On Days 252 and 546, collect blood samples for clinical laboratory tests, including:
 - Hematology;
 - Thyroid function tests.
- On Days 252 and 546, collect urine sample for urinalysis;
- On Days 21, 126, 252, 399, and 546, collect a plasma PK sample pre-dose (within 1 hour of planned study drug dosing);
- On Days 21, 126, 252, 399, and 546, collect a urine PK sample pre-dose (within 1 hour of planned dosing start);
- Perform ophthalmology examinations on Day 21 (if baseline examination was not completed prior to the Day 21 visit), once between Days 231(\pm 3) and 272 at a CAS, and once between Days 546(\pm 3) and 560 at a CAS;
- Complete the pharmacoeconomics questionnaire on Day 21, if not completed prior to the Day 21 visit;
- At all dosing visits, obtain information on concomitant medications;
- At all dosing visits, document any AEs.

Following the completion of all required pre-dose activities and assessments, administer the study drug at all dosing visits, as described in [Section 6.2.1.2](#).

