6.2.4 Follow-Up Visits

Patients will return to the study site for 2 follow-up visits, 21 days and 56 days after receiving their last dose of study drug. If a patient enrolls in the extension study, they will only have to complete the 21-day follow-up assessments (End of Study [EOS]; Day 567) and not the 56-day follow-up assessments (Day 602). Patients who do not enroll in the extension study will need to complete both follow-up visits (EOS [Day 567] and Day 602).

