6.2.4.1 Twenty-One-Day Follow-up Visit (End of Study)

The following procedures will be performed at the 21-Day Follow-up visit (EOS; Day 567).

- Perform a physical examination;
- Measure weight;
- Measure vital signs;
- Collect blood sample for serum TTR protein, RBP, and vitamin A. Additionally, aliquots of serum samples will be taken for long-term frozen storage, to permit testing of additional proteins related to FAP;
- Perform a pregnancy test (for females of child-bearing potential only);
- Obtain information on concomitant medications;
- Document any AEs.

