8.5 Adverse Event Reporting Period

AEs and SAEs will be reported according to the following timeframes:

- For patients who complete the study, AEs will be assessed through the End of Study visit on Day 567 or the Follow-up visit on Day 602 (depending whether or not the patient plans to roll over to the open-label extension study). All AEs that occur after the start of study drug administration on Day 0 must be reported in detail on the appropriate CRF page and followed to satisfactory resolution, or through the end of study visit on Day 567 or Day 602 (depending whether or not the patient plans to roll over to the open label extension study) after the last dose of study drug administration. SAEs will be followed through the end of study visit on Day 567 or Day 602 (depending whether or not the patient plans to roll over to the open label extension study), or until satisfactory resolution, or until the SAE is considered by the Investigator to be chronic or the patient is stable, whichever occurs first.
- For patients who meet the criteria for Rapid Disease Progression at Month 9 and receive their last dose of study drug on Day 252 but remain on the study, AEs will be followed through Day 294. Following Day 294, only study-procedure-related AEs will be collected (e.g., skin-biopsy-related AE, venipuncture-related AE). SAEs will be followed by the Investigator until satisfactory resolution or the Investigator deems the SAE to be chronic or stable.

- For patients who withdraw from the study early, ongoing AEs will be followed until resolution or 28 days from last dose, whichever occurs first. SAEs will be followed by the Investigator until satisfactory resolution or the Investigator deems the SAE to be chronic or stable.

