1.2.5. Unblinding

Unblinding is only to occur in the case of patient emergencies or when necessary from a regulatory reporting perspective (e.g., Suspected Unexpected Serious Adverse Reaction [SUSAR] occurring in the EU), and at the conclusion of the study.

Patients who discontinue study drug at 9 months due to rapid disease progression will remain blinded throughout the remainder of the study.

In the event that the Investigator requests to know a patient's study treatment assignment, the Investigator is instructed to contact the Contract Research Organization (CRO) Medical Monitor to discuss the need for unblinding. In case of an emergency, the treatment allocation for each patient will be available from the unblinded site personnel, pharmacist, or the IRS system.

If a patient becomes pregnant or seriously ill during the study, the blind should be broken only if knowledge of the treatment administered will affect treatment options available to the patient. Before breaking the blind, the Principal or Sub-investigator should attempt to contact the CRO Medical Monitor. If the Medical Monitor is immediately unreachable, the Principal or Sub-investigator should break the blind as necessary using the code breaking information provided and contact the CRO Medical Monitor as soon as possible. A record will be kept of when the blind was broken, who broke it, and why.

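### SAP 3.11 permits unblinding and final safety tables before the last Day 567/602 safety visits are complete, and confines later safety data to listings

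*SAP*

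**What the plan says.** SAP 3.11 sets the order of events. The starting point is "After the last patient completes the 18-month efficacy assessment or the 18-month efficacy visit window per protocol has elapsed". The sponsor then prepares for the final analysis, and "The study will then be unblinded and the final analysis will be conducted". Safety data that arrive later are covered by one sentence: "If there is additional safety data collected after the final analysis, the data will be presented in listings only". The section gives no length for the preparation step and names no safety visit as a condition.

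Protocol 6.2.2 places the efficacy visits: "9-month and 18-month efficacy assessments (occurring on Days 253-272 and Days 553-560, respectively". Safety follow-up runs beyond that. Protocol 6.2.4 says: "Patients will return to the study site for 2 follow-up visits, 21 days and 56 days after receiving their last dose of study drug". Protocol 6.2.4.1 identifies the first of these as the "21-Day Follow-up visit (EOS; Day 567"), where EOS stands for End of Study. The second, on Day 602, is only for patients who do not enter the extension. For patients who complete the study, protocol 8.5 says "AEs will be assessed through the End of Study visit on Day 567 or the Follow-up visit on Day 602", depending on whether they roll over.

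Both documents restrict unblinding. Protocol 4.4.3 and SAP 1.2.5 allow it for patient emergencies, for regulatory reporting, "and at the conclusion of the study".

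**The concern.** The trigger in SAP 3.11 is an efficacy milestone, but the analysis it releases includes the safety tables. When the trigger is met, the last patients still have scheduled safety visits to come. Two things are at stake.

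- **Completeness of the by-arm tables.** SAP 4.6.2 tabulates treatment-emergent events by arm, and SAP 4.6.3 tabulates laboratory shifts and liver-test categories by arm. Under the late-data sentence, information collected after the analysis never reaches those tables, even when it meets the SAP's own definitions.
- **Blinded rating.** Severity and causality are investigator judgements (protocol 8.6 and 8.7), and SAP 4.6.2 tabulates events by both. Causality can also decide whether an event is counted at all. Under SAP 4.6.2, an event present at baseline becomes treatment-emergent if the investigator later considers it drug-related, up to the end of the study. Section 3.11 does not say that the people making these judgements stay blinded after the study is unblinded.

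The rule tying planned unblinding to the study's conclusion should settle the second matter. It does not, because neither document says when the study concludes.

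**Working it through.** All days are on the protocol scale (first dose Day 0, last scheduled dose Day 546). The SAP scale is one day higher.

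**Check of the scale.** The follow-up visits fall at 546 + 21 = Day 567 and 546 + 56 = Day 602. With the 42-day screening period, (42 + 602) / 30.44 = 21.2 months, which reproduces the roughly 21 months of participation stated in protocol section 6.

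**Inputs**
- 18-month efficacy visit: Days 553 to 560 (protocol 6.2.2).
- Visit windows: ±7 days for Day 567 and ±10 days for Day 602 (protocol Table 1-2).
- Treatment-emergent window: through 28 days after the last dose (SAP 4.6.2), so 546 + 28 = Day 574.

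**Outstanding when the efficacy window closes on Day 560**
- Day 567 visit: 567 − 560 = 7 days (0 to 14 with its window).
- Day 602 visit, non-extension patients only: 602 − 560 = 42 days (32 to 52 with its window).
- Treatment-emergent window: 574 − 560 = 14 of 28 days. Patients entering the extension have adverse events assessed only to Day 567, so for them the nominal exposure is 7 days.

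**What cannot be lost.** A new event with onset on Days 575 to 602 is outside the 28-day window and stays out of the treatment-emergent tables whenever they are run. The exception is the baseline-event clause of SAP 4.6.2, which stays open to the end of the study.

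**Laboratory data.** The shift tables in SAP 4.6.3 use the worst post-baseline category, and the liver-test table counts any post-baseline time point; neither has a 28-day limit. Chemistry is drawn before dosing on Day 546 (protocol 6.2.2) and again on Day 602 (6.2.4.2). It is not listed at the 18-month efficacy visit (6.2.3) or on Day 567 (6.2.4.1). For a patient who takes the Day 546 dose and does not enter the extension, Day 602 is therefore the only scheduled chemistry after the last dose.

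**How much preparation time closes the gap.** Counting from Day 560, 14 days reach the end of the treatment-emergent window and the latest permitted Day 567 visit. It takes 612 − 560 = 52 days to pass the latest permitted Day 602 visit.

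**Patients involved.** The enrolment period is not given. Assume 200 patients enrolled evenly over 24 or 12 months, and no preparation time:
- Within 7 days of the last patient: 200 × 7 / (24 × 30.44) = 1.9, to 200 × 7 / (12 × 30.44) = 3.8.
- Within 14 days: 200 × 14 / 730.56 = 3.8, to 200 × 14 / 365.28 = 7.7.
- Within 42 days: 200 × 42 / 730.56 = 11.5, to 200 × 42 / 365.28 = 23.0. Only the unknown share not entering the extension counts here.

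Early withdrawals and any preparation time lower all of these figures.

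**When the study concludes.** Two readings are open. Protocol 4.5 and SAP 1.2.4 count a patient as having completed the study once procedures through the 18-month efficacy visit are done, which matches the 3.11 trigger. Against that, the protocol names Day 567 the End of Study visit, and protocol section 6 counts participation up to the 56-day visit. The first passages define a patient's completion status; they do not say when the trial ends.

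**The case against.** The strongest reply is that SAP 3.11 only permits early unblinding. A preparation step comes first, and SAP 2.2 requires the protocol deviation file to be final before database lock and unblinding, so some cleaning and a lock come in between. With 52 days of preparation, no scheduled visit would be outstanding. The late-data sentence is conditional, and the data it covers are still reported in listings. Safety summaries are descriptive (SAP 4.6), and running the final analysis after the last primary endpoint visit is a stated, prespecified choice.

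Most of this stands, and it rules out several readings that a reader might infer:
- *That the SAP schedules unblinding before the last safety visits.* It sets no date.
- *That SAP 3.11 directly contradicts the unblinding rule.* The rule rests on an undefined term, and one supportable reading agrees with 3.11.
- *That investigators receive treatment codes at this point.* Nothing says so; equally, nothing says they remain blinded.
- *That the primary comparison is exposed.* The scheduled endpoint visit is finished before the trigger.

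What the reply does not remove is the dependence on an unstated interval. The plan itself foresees safety data arriving after the analysis, and its rule for them conflicts with the table definitions in SAP 4.6.2 and 4.6.3.

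**Conclusion.** The point holds as a gap in the plan. SAP 3.11 allows the study to be unblinded and the safety tables made final while the last patients' safety follow-up is open. Up to 14 days of treatment-emergent onset, later causality judgements on baseline events, and the only scheduled post-last-dose chemistry for patients not entering the extension could then stay out of the by-arm tables. The last severity and causality ratings could be made after unblinding. This is hard to square with protocol 4.4.3 and SAP 1.2.5, given the Day 567 label, but it is not a proven breach of them.

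The size is probably small: about 4 to 8 patients within 14 days of the last patient, under the enrolment assumption above and with no preparation time. It could be none. The Day 602 group could be larger, but extension uptake is unknown. This is a low-severity improvement, worth making because it costs little.

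**What to change.** In SAP 3.11:
- Replace the listings-only rule with a commitment to rerun the by-arm safety tables on the complete safety data, through the last Day 567 or Day 602 visit.
- State that investigators and site raters stay blinded until the safety visit of their last patient has been recorded.
- Define when the study concludes, and use that definition in SAP 1.2.5, SAP 3.11 and protocol 4.4.3.

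The efficacy trigger need not move. The cost is one rerun of the safety tables. Moving the trigger itself to the last safety visit would be a separate and more debatable choice: counted from Day 560, it could add 42 days nominally and up to 52 with the visit window (52 / 7 = 7.4 weeks).

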4. STUDY ANALYSES

4.1. Patient Disposition

Patient disposition will be tabulated and will include the following parameters: the number of patients in each analysis population, the number of patients randomized, the number of patients treated, the number of patients completing treatment, the number of patients completing study, the number of patients who discontinued treatment and primary reasons for treatment discontinuation, the number of patients who withdrew prior to completing the study and primary reasons for withdrawal, the number of patients meeting the protocol specified criteria for rapid disease progression, the number of patients who discontinued treatment but completed the study, and the number of patients who completed treatment but withdrew prior to completing the study. Patient disposition will be presented by randomized treatment arm (patisiran and placebo) and overall.

The number and percent of patients enrolled by country and site will be summarized by randomized treatment arm and overall. The number and percent of patients in each randomization stratification factor recorded in IVR, and a comparison of the number and percent of patients in each randomization stratification factor in IVR versus the clinical database will be summarized by randomized treatment arm and overall.

Data listings of treatment/study completion information including the reason for treatment discontinuation and/or study withdrawal will be presented.

